2.2 Secondary Objectives

- To determine the better/"adequate" ⁸⁹Zr-DFO-MSTP2109A mass amount for tumor imaging (10 or 20 mg) .
- To determine optimal time relative to ⁸⁹Zr-DFO-MSTP2109A administration for tumor imaging.
- To use quantitative biodistribution data of ⁸⁹Zr-DFO-MSTP2109A uptake to perform dosimetry estimates.
- To correlate ⁸⁹Zr-DFO-MSTP2109A uptake in tumors with STEAP1 antigen expression by IHC
- To explore whether ⁸⁹Zr-DFO-MSTP2109A PET imaging results are related to patient outcome in patients being treated with DSTP3086S.

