The drug conjugate DSTP3086S has been used in 26 patients as of 08/22/2012 as part of an ongoing Phase I multi-center clinical trial - MSKCC protocol 11-016. Currently, enrollment is occurring at 2.8 mg/kg. Only two DLT have been observed consisting of transaminitis at the 2.25 mg/kg, and elevated liver enzymes in a patient treated at a dose level of 2.8 mg/kg. Reversible liver toxicity was observed in pre-clinical assessments with DSTP3086A and likely represents toxicity attributable to the drug conjugate. Otherwise, treatments have been very well tolerated with very mild side effects possibly related to treatment such as Gr1 hypotension constipation or diarrhea. Other ⁸⁹Zr-labeled antibodies have been used in patients with good tumor localization and tolerated well (Borjesson, Jauw et al. 2006; Borjesson, Jauw et al. 2009; Dijkers, Munnink et al. 2010). As of date, the protocol continues to accrue.

3.2.2.1 ⁸⁹Zirconium

⁸⁹Zr is an attractive metallo-radionuclide for use in immuno-PET due to favorable decay characteristics. It has a 78.4h half life and a 22.7% positron yield.

Standardized methods for the routine production and isolation of high-purity and high-specific-activity ⁸⁹Zr using a small cyclotron are reported. Optimized cyclotron conditions reveal high average yields of 1.52 ± 0.11 mCi/muA*h at a proton beam energy of 15 MeV and current of 15 muA using a solid, commercially available ⁸⁹Y-foil target (0.1 mm, 100% natural abundance). ⁸⁹Zr was isolated in high radionuclidian and radiochemical purity (>99.99%) as (⁸⁹Zr)Zr-oxalate by using a solid-phase hydroxamate resin with >99.5% recovery of the radioactivity. The effective specific activity of ⁸⁹Zr was found to be in the range of 5.28–13.43 mCi/microg (470–1195 Ci/mmol) of zirconium.

New methods for the facile production of (⁸⁹Zr) Zr-chloride are reported. Radiolabeling studies using the trihydroxamate ligand desferrioxamine B (DFO) gave 100% radiochemical yields in <15 min at room temperature, and *in vitro* stability measurements confirmed that (⁸⁹Zr) Zr-DFO is stable with respect to ligand dissociation in human serum for >7 days. Small-animal PET imaging studies have demonstrated that free ⁸⁹Zr (IV) ions administered as (⁸⁹Zr) Zr-chloride accumulate in the liver, whilst (⁸⁹Zr) Zr-DFO is excreted rapidly via the kidneys within <20 min.

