4.3 Intervention

The intervention is the administration of a single dose of the ^{89}Zr -DFO-MSTP2109A tracer for imaging purposes. In Cohort 1A or 1B, after administration of the experimental tracer, the patient will undergo up to four PET scans during the 7 days post injection, whole body probe measurements and pharmacokinetics. In Cohort 2, patients will undergo injection of ^{89}Zr -DFO-MSTP2109A, and they will undergo one PET scan from top of skull to mid thigh (this may be adjusted based on known extent of disease) and no pharmacokinetics will be performed. The primary population will be those who are planning to enroll in the therapeutic trial using DSTP3086S (11-016), although for Cohort 1A, 1B and potentially Cohort 2 patients that meet the inclusion criteria may be enrolled even if not considered for DSTP3086S therapy. No clinical management decisions will be made based on ^{89}Zr -DFO- MSTP2109A imaging. Patients may not be re-imaged on this trial.

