14.1 BIOSTATISTICS

14.2 Primary Objective

The primary objective of this protocol is to determine the feasibility, safety and tolerability of single dose administration of ^{89}Zr -DFO-MSTP2109A antibody.

A patient with STEAP1 positive tumor will be considered antibody-imaging-positive if 20% or more of the active lesions are detectable (STEAP1 positivity is an eligibility criterion for protocol 11-016 which forms the basis of eligibility for this protocol; see section 6 for details). Active lesion means any lesion that was identified by conventional imaging methods and clinical data at baseline. We have selected a low threshold of 20% for this first imaging study for 3 reasons: 1) we do not know what the heterogeneity of antigen expression is within a number of lesions in the same patient; 2) we will consider positive any lesion based on conventional clinical imaging criteria, in which case some lesions considered positive may be false positive and more importantly 3) our main emphasis is to evaluate whether patients whose tumor images are positive with ^{89}Zr -DFO-MSTP2109A are more likely to have a response to the antibody based drug conjugate used under

MEMORIAL SLOAN-KETTERING CANCER CENTER IRB PROTOCOL

IRB#:12-178 A(3)

protocol 11-016. Thus, we do not want to discard this agent if we can use it as a **theranostic** (defined as an agent that is integrated into the drug development process so as to guide patient selection and drug development) for the development of the antibody base drug conjugate being used under protocol 11-016. Nonethe less, we intend to evaluate treatment response of all available lesions in this way we will maximize our ability to determine the relationship between uptake of antibody and response.

If, for any patient, there is evidence of an “antigen sink” based on rapid clearance < 50 h or $Vd > 3$ times plasma volume, we will consider a patient antibody-imaging-positive if 20% or more of the active lesions are visualized. The presence of an “antigen sink” may bind a significant amount of antibody and make less available for binding to tumor.

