14.3 Secondary objectives

One of our secondary exploratory objectives is to estimate the uptake in tumors. We will present lesion-based summary statistics for the uptake adjusted for clustering. Another secondary objective is to correlate ⁸⁹Zr-DFO-MSTP2109A imaging to response to treatment in those patients recruited to protocol 11-016 DSTP3086S ADC. Outcome measures to be correlated include those that are outlined in the parent protocol 11-016 and include PSA response, RECIST response, presence or absence of new bone scan lesion and progression free survival. We will use Kaplan-Meier estimates and 95% confidence intervals to correlate these outcomes with imaging response.

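### Section 14.3 leaves the imaging predictor of ADC response undefined, and the only grouping available for its Kaplan-Meier curves would leave few imaging-negative men

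*Combined protocol and SAP*

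**What the plan says.** Section 2.2 lists the aim as a secondary one, to explore whether "PET imaging results are related to patient outcome in patients being treated with DSTP3086S". Section 14.2 gives it more weight. In defending the low positivity threshold it states that "our main emphasis is to evaluate whether patients whose tumor images are positive" are more likely to respond to the ADC given under protocol 11-016. It adds a lesion-level intention: "we intend to evaluate treatment response of all available lesions in this way we will maximize our ability to determine the relationship" between antibody uptake and response.

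The patient-level imaging rule in section 14.2 is that a man with a STEAP1-positive tumour "will be considered antibody-imaging-positive if 20% or more of the active lesions are detectable".

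Section 14.3 names the outcomes, taken from 11-016: PSA response, RECIST response, new bone scan lesions and PFS. The method is: "We will use Kaplan-Meier estimates and 95% confidence intervals to correlate these outcomes with imaging response". It also plans lesion-based summaries of uptake that allow for clustering. It gives no definition of imaging response, no number of treated men, no test and no power.

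Section 4.3 makes men bound for 11-016 the primary population, but in cohorts 1A and 1B, and potentially cohort 2, "patients that meet the inclusion criteria may be enrolled even if not considered for DSTP3086S therapy".

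**The concern.** The method in section 14.3 does not deliver what section 14.2 promises, in four respects.

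- **Predictor.** Kaplan-Meier estimates compare groups, so imaging response has to become a grouping. The only one that section 14 offers at patient level is the 20% rule.
- **Contrast.** Every man is to be STEAP1 positive, and one lesion in five is enough to be called positive. Cohort 2 opens only after at least 4 of 6 men are positive. The negative group is likely to be small.
- **Outcomes.** Kaplan-Meier suits PFS. It does not suit PSA response, RECIST response or a new bone lesion recorded as present or absent.
- **Lesions.** Uptake is summarised with clustering but is not related to any outcome, so the lesion-level intention has no analysis.

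What is at stake is the question used to justify the threshold. A comparison with a handful of negatives could show nothing even if uptake and response were related, and might then be taken as evidence against using the tracer to select patients.

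**Working it through.** **1. The plan's own figures (section 14.2).**
- Cohort 2 precision: 1.96 × √(0.75 × 0.25 / 15) = 0.219. The plan says ±22%.
- Cohort 1A rule, probability of 3 or fewer positives among 6: 0.821 at a true rate of 40% and 0.169 at 75%. The plan says more than 82% and less than 17%.

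All three reproduce. There is no corresponding figure for the ADC-response aim.

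**2. Number treated.** Enrolment is at most 6 + 15 = 21 without cohort 1B, or 6 + 6 + 15 = 27 with it. The analysis set is men recruited to 11-016 from any cohort, and its size is not given. I take 15 and 27 as illustrations; it could be below 15.

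**3. Expected negatives** = 0.25 × number treated, using the plan's 75% as an assumption.
- 15 treated: 3.75 (binomial 95% range 1 to 7; probability of 3 or fewer 0.46).
- 21 treated: 5.25 (2 to 9).
- 27 treated: 6.75 (3 to 11).
- If only half of 15, 21 or 27 were treated: 1.9, 2.6 and 3.4.

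**4. Precision with that split.**
- Response rate among negatives, none responding: the exact upper 95% limit is 1 − 0.025^(1/n). For n = 4 this is 0.60, and for n = 7 it is 0.41. One responder in 4 gives 1% to 81%.
- PFS, in the best case where every man has an event: SE of the log hazard ratio ≈ √(1/d₁ + 1/d₂).
  - 11 v 4 events: √(0.0909 + 0.25) = 0.584, so the 95% limits are the estimate divided and multiplied by exp(1.96 × 0.584) = 3.14. An observed hazard ratio of 0.5 would carry an interval of 0.16 to 1.57.
  - 20 v 7 events: √(0.05 + 0.1429) = 0.439, factor 2.36. The interval would be 0.21 to 1.18.

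**5. A yardstick only, since the plan contains no test.** Probability that a two-sided Fisher test at 5% separates assumed response rates (not in the documents):

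| Positives v negatives | 50% v 10% | 60% v 10% | 70% v 10% |
|---|---|---|---|
| 11 v 4 | 8% | 20% | 41% |
| 20 v 7 | 33% | 58% | 79% |

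**6. Does a graded predictor help?** Simulation with a continuous outcome, comparing a rank correlation with a Mann-Whitney test on a 75/25 split. The share reaching p < 0.05 depends on the assumed shape:

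| Assumed relation | n | Graded | Split |
|---|---|---|---|
| Linear, correlation 0.5 | 15 | about 45% | about 23% |
| Linear, correlation 0.5 | 27 | about 73% | about 45% |
| Step of 1.33 SD at the cut | 15 | about 30% | about 48% |
| Step of 1.33 SD at the cut | 27 | about 51% | about 80% |

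The graded measure gains if response rises steadily with uptake, and loses if the effect is a jump exactly at the threshold. The documents do not say which to expect, so both summaries are worth having.

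**The case against.** The strongest reply is that this is an exploratory aim in a small first imaging study. Section 14.3 promises estimates with confidence intervals and makes no claim of power, so low power breaks nothing. That stands, and the point here is about specification and precision.

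Several stronger readings are tempting, and the documents do not support them.

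- **That 15 men will be treated, with 4 negative.** Fifteen is the enrolment cap of cohort 2. The treated men may come from any cohort, and their number is unstated.
- **That 75% positivity is expected.** It is a feasibility criterion and a planning value.
- **That the plan has chosen to test a positive/negative split.** No test is named and imaging response is undefined. The split is an inference from the use of Kaplan-Meier.
- **That lesion uptake is ignored, or that SUV is available for every lesion.** Section 14.3 does summarise uptake with clustering. Section 12.0 measures SUV in lesions identified. If that means lesions seen on the tracer scan, an average SUV would drop the lowest-uptake lesions and would not exist for a man with none detected.
- **That ADC dose confounds the comparison.** Section 3.2.2 reports toxicity at two dose levels in 11-016 and says "Currently, enrollment is occurring at 2.8 mg/kg". It does not show how dose varies among the men imaged here.
- **That no relation could be shown.** With 20 v 7 men and response rates of 70% v 10%, the yardstick above reaches 79%.

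The step-effect result also stands: a graded predictor is not better in every case.

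**Conclusion.** The concern holds as a gap between sections 14.2 and 14.3. The imaging predictor is undefined and Kaplan-Meier fits only one of the four listed outcomes. The lesion-level analysis announced in section 14.2 has no method.

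If the 20% rule supplies the groups, the negative group would be about 4 of 15 or 7 of 27 treated men at 75% positivity, and fewer if many enrolled men never receive the ADC. Estimates for that group would be very imprecise. Section 9.3 calls a man positive if any active lesion is seen; if that rule were applied, there could be fewer negatives still.

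The counts rest on the plan's 75% and on assumed numbers treated. The response rates, hazard ratio and shapes of relation are illustrative. The missing definition and the missing lesion-level model do not depend on any of these. This is a cheap improvement to an exploratory analysis and does not call for a larger trial.

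**What to change.** Amend section 14.3, all as exploratory estimation:

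1. State the expected number of ADC-treated men and define imaging response. Use the fraction of active lesions detected as the main graded predictor. It can be computed for every scanned man, since section 9.3 already tabulates lesions and their status. Relate it to percent PSA change and best RECIST change (rank correlation) and to PFS (Cox model), each with a 95% interval.
2. Add lesion SUV as a further predictor. Measure region-of-interest uptake also at active conventional-imaging sites not seen on the tracer scan, so that low-uptake lesions stay in.
3. Specify the lesion-level analysis: tracer uptake against lesion response, with a patient random effect and scans at comparable times across cohorts. Limit size change to measurable soft-tissue lesions, because section 1.0 says that bone lesions on CT do not reflect active tumour size.
4. Report binary outcomes by positive/negative status as proportions with exact intervals. Keep Kaplan-Meier by that status for PFS as description, and state that no visible difference there is not evidence against prediction.
5. Tabulate ADC dose and adjust for it only if it varies among the imaged men.

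The cost is analysis wording, some extra region-of-interest measurement and more exploratory estimates to report. It assumes that 11-016 records the underlying PSA and lesion measurements. The graded analysis would be less sensitive than the split if the true relation is a step at the threshold, which is a reason to keep both.

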15.1 RESEARCH PARTICIPANT REGISTRATION AND RANDOMIZATION PROCEDURES

15.2 Research Participant Registration

Confirm eligibility as defined in the section entitled Criteria for Patient/Subject Eligibility.

Obtain informed consent, by following procedures defined in section entitled Informed Consent Procedures.

During the registration process registering individuals will be required to complete a protocol specific Eligibility Checklist.

All participants must be registered through the Protocol Participant Registration (PPR) Office at Memorial Sloan-Kettering Cancer Center. PPR is available Monday through Friday from 8:30am – 5:30pm at [contact]. Registrations must be submitted via the PPR Electronic Registration System (<http://ppr/>). The completed signature page of the written consent/RA or verbal script/RA, a completed Eligibility Checklist and other relevant documents must be uploaded via the PPR Electronic Registration System.

15.3 Randomization

This research study does not require randomization procedures.

16.1 DATA MANAGEMENT ISSUES

A Research Study Assistant (RSA) will be assigned to the study. The responsibilities of the RSA include project compliance, data collection, abstraction and entry, data reporting, regulatory monitoring, problem resolution and prioritization, and coordinate the activities of the protocol study team.

The data collected for this study will be entered into a secure database. Source documentation will be available to support the computerized patient record.

Study personnel will record clinical data in each patient's source documents (i.e., the patient's medical record).

MEMORIAL SLOAN-KETTERING CANCER CENTER IRB PROTOCOL

IRB#:12-178 A(3)

The investigator will maintain adequate and accurate records to enable the conduct of the study to be fully documented and the study data to be subsequently verified. After study closure, the investigator will maintain all source documents, study-related documents, and the data stored in the database used for data collection. Records will be retained and securely stored for a minimum of 2 years after the completion of all study activities.

Data will be entered throughout the duration of the trial as patients are enrolled. Accrual is expected to last 2 years.

16.2 Quality Assurance

Regularly scheduled registration reports will be generated to monitor patient accruals and the completeness of registration data. Routine data quality reports will be generated to assess missing data and inconsistencies. Accrual rates and the extent and accuracy of evaluations and follow-up will be monitored periodically throughout the study period, and potential problems will be brought to the attention of the principal investigator for discussion and action.

Random-sample data quality and protocol compliance audits will be conducted by the study team at least once a year, more frequently if indicated.

16.3 Data and Safety Monitoring

The data and safety monitoring (DSM) plans at MSKCC were approved by the National Cancer Institute in September 2001. The plans address the policies set forth by the NCI in the document entitled *Policy of the National Cancer Institute for Data and Safety Monitoring of Clinical Trials*, which can be found at <http://cancertrials.nci.nih.gov/clinicaltrials>. The DSM plans at MSKCC were established and are monitored by the Office of Clinical Research. The MSKCC DSM plans can be found on the MSKCC Intranet at: <http://mskweb5.mskcc.org/intranet/html/70775.cfm>.

There are several different mechanisms by which clinical trials are monitored for data, safety, and quality. There are institutional processes in place for quality assurance (e.g., protocol monitoring, compliance and data verification audits, therapeutic response, and staff education on clinical research quality assurance) and departmental procedures for quality control, and there are two institutional committees that are responsible for monitoring the activities of our clinical trials programs. The committees: *Data and Safety Monitoring Committee (DSMC)* for Phase I and II clinical trials, and the *Data and Safety Monitoring Board (DSMB)* for Phase III clinical trials, report to the MSKCC Research Council and Institutional Review Board.

During the protocol development and review process, each protocol will be assessed for its level of risk and degree of monitoring required. Every type of protocol (e.g., NIH sponsored, in-house sponsored, industrial sponsored, NCI cooperative group, etc.) will be addressed, and the monitoring procedures will be established at the time of protocol activation.

For this protocol, we will use the following patient safety monitoring plan and monitoring for adverse events, in terms of the test performed and their timing relative to injection (see Table 1 and 2). Patient will be observed closely during infusion and serial vital signs will be monitored every half hour for at least 2 h or later if the patient remains in the department. Patients will be queried for adverse events up to 6-8 days after infusion.

Safety reviews will be performed by the MSKCC-DSMC with yearly review by the IRB.

17.1 PROTECTION OF HUMAN SUBJECTS

This study will be conducted in compliance with the protocol, GCP guidelines established by the International Conference on Harmonization, and the ethical standards set forth in the Declaration of Helsinki 2004 (available at: www.laakariliitto.fi/e/ethics/helsinki.html).

A limited waiver of authorization will be utilized to effectively screen and track patients in screening, however the recruitment process outlined presents no more than minimal risk to the privacy of the patients who are screened and minimal protected health information (PHI) will be maintained as part of a screening log.

This protocol does not have therapeutic intent and does not offer patients therapeutic benefit. This will be clearly conveyed to patients when communicating the potential toxicities/side effects of participating in this trial. Participation in the trial is voluntary and there will be no financial benefit (or burden) for the patients. Participants will not be charged for ^{89}Zr -DFO-MSTP2109A PET scans, whole body probe counts, radiotracer drugs, extra blood draws (to measure radiotracer activity), and optional biopsies.

17.2 Privacy

MSKCC's Privacy Office may allow the use and disclosure of protected health information pursuant to a completed and signed Research Authorization form. The use and disclosure of protected health information will be limited to the individuals described in the Research Authorization form. A Research Authorization form must be completed by the Principal Investigator and approved by the IRB and Privacy Board (IRB/PB).

17.3 Serious Adverse Event (SAE) Reporting

Any SAE must be reported to the IRB/PB as soon as possible but no later than 5 calendar days. The IRB/PB requires a Clinical Research Database (CRDB) SAE report be submitted electronically to the SAE Office at [contact]. The report should contain the following information:

Fields populated from CRDB:

- Subject's name (generate the report with only initials if it will be sent outside of MSKCC)
- Medical record number
- Disease/histology (if applicable)
- Protocol number and title

Data needing to be entered:

- The date the adverse event occurred
- The adverse event
- Relationship of the adverse event to the treatment (drug, device, or intervention)
- If the AE was expected
- The severity of the AE
- The intervention
- Detailed text that includes the following
 - A explanation of how the AE was handled
 - A description of the subject's condition
 - Indication if the subject remains on the study
 - If an amendment will need to be made to the protocol and/or consent form.

MEMORIAL SLOAN-KETTERING CANCER CENTER IRB PROTOCOL

IRB#:12-178 A(3)

The PI's signature and the date it was signed are required on the completed report.

For IND/IDE protocols:

The CRDB AE report should be completed as above and the FDA assigned IND/IDE number written at the top of the report. If appropriate, the report will be forwarded to the FDA by the SAE staff through the IND Office.

17.2.1

SAE Reporting To Genentech:

All written IND Safety Reports submitted to the FDA by the Investigator must also be faxed to Genentech Drug Safety:

- Serious AE reports that are related to the ⁸⁹Zr-MSTP2109A will be transmitted to Genentech within fifteen (15) calendar days of the Awareness Date.
- Serious AE reports that are unrelated to the ⁸⁹Zr-MSTP2109A will be transmitted to Genentech within thirty (30) calendar days of the Awareness Date.

Investigators must report all SAEs to Genentech within the timelines described above. The completed MedWatch/case report should be faxed immediately upon completion to Genentech Drug Safety at:

**[contact]
OR
[contact]**

